8.1.1. Footnotes for the Schedule of Events Tables

EOS = end of study; EOT = end of treatment; U = urine; Core lipid panel = TC, calculated LDL-C, HDL-C, TGs, and non-HDL-C; Specialty lipid panel = ApoB, ApoA-1, ratio ApoB/ApoA-1, and Lp(a).

1. All patients will be reminded of protocol-specified contraception use and pregnancy reporting.
2. All laboratory samples should be collected before the administration of study drug. All samples should be collected following at least an 8-hour fast.
3. Electrocardiograms should be performed before blood is drawn during visits requiring blood draws.
4. On dosing days, PK collection should occur pre-dose for group A and prior to IV infusion and at the end of the IV infusion for group B.
5. LDL-R function samples will be collected from a sub-set of patients based on enrollment and will be determined by IWRS.

- [REDACTED]
- [REDACTED]
- [REDACTED]
7. For SC dosing, patients will be observed at the clinical site for at least 30 minutes following each SC study drug administration. For IV dosing, patients will be monitored for at least 60 minutes following the end of each IV study drug administration.
 8. Starting at W1 and every odd visit week (ie, W3, W5, W7, etc) thereafter, visiting home nurses may administer study drug for those patients randomized to Group A.
 9. WOCBP will be provided urine pregnancy tests with instructions to test for pregnancy at home.
 10. All subjects will be contacted by phone to query LMT compliance, inquire about AEs or changes to concomitant medications, confirm required contraception use and remind patients of pregnancy reporting. Women of childbearing potential will report the results of their home urine pregnancy test. All patients will also be queried regarding their low fat diet.
 11. Vital signs should be recorded prior to SC injection or IV infusion, and 30 minutes and 60 minutes post-IV infusion.

8.1.2. Early Termination Visit

Patients who withdraw or are withdrawn from the study before EOT visit

Patients who withdraw or are withdrawn from the study before the week 16 visit, will be asked to return to the clinic for 2 visits: once for an early termination/EOT visit, consisting of the EOT assessments described in [Table 3](#) and [Table 4](#), and again at the EOS visit. The EOT visit should take place within 5 days of treatment discontinuation, if possible. A final EOS visit should take place with assessments as specified in the EOS visit (ie, follow-up visit) at 24 weeks after the last dose of study drug ([Table 6](#) and [Table 7](#)).

Patients who withdraw or are withdrawn from the study after EOT Visit

Patients who are withdrawn from the study after the EOT visit (week 16 for SC group or week 24 for IV group) will be asked to return to the clinic for early termination assessments/EOS, only. The EOS visit should take place with assessments as specified in the EOS visit (ie, follow-up visit) at 24 weeks after the last dose of study drug.

Sexually active patients who discontinue the study prematurely should have an unscheduled visit to remind patients to maintain highly effective contraceptive measures for 24 weeks after the last dose of study drug. At this visit, WOCBP will be provided urine pregnancy tests with instructions to test for pregnancy Q4W until the EOS visit. All patients should also be notified of Q4W follow-up phone calls to confirm contraception use, remind them of pregnancy reporting, and to obtain the results of the urine pregnancy test.

8.1.3. Unscheduled Visits

All attempts should be made to keep patients on the study schedule. Unscheduled visits may be necessary to repeat testing following abnormal laboratory results, for follow-up of AEs, or for any other reason, as warranted.

8.2. Study Procedures**8.2.1. Procedures Performed Only at the Screening/Baseline Visit**

The following procedures will be performed for the sole purpose of determining study eligibility or characterizing the baseline population:

- Demographics,
- Past medical/surgical history, alcohol/smoking habits
- Medication history,
- Medication adjustments
- Height, weight, vital signs, physical examination, ECG
- Hepatitis B and C serology,
- TSH,
- FSH

8.2.2. Efficacy Procedures

All laboratory samples will be collected before the dose of study drug is administered.

Blood samples for lipid panels should be collected in the morning, in fasting condition (ie, overnight, at least 8 hours fast, only water) for all clinic visits. Alcohol consumption within 48 hours, and smoking or intense physical exercise within 24 hours, preceding blood sampling are discouraged.

Note: If the patient is not in the fasting condition, the blood sample may not be collected and a new appointment can be scheduled the day after (or as close as possible to this date) with a

reminder to be fasted. Patients who are not fasted should 1) be reminded that they should fast, and 2) should be seen by study staff the next day or close as possible in fasted state.

Total-C, HDL-C, TG, ApoB, ApoA-1, Lp(a), and ApoCIII will be directly measured by the central laboratory. LDL-C will be calculated using the Friedewald formula. If TG values exceed 400 mg/dL (4.52 mmol/L), LDL-C will be measured via the beta quantification method (rather than via the Friedewald formula). If the LDL-C value is less than 25 mg/dL (0.65 mmol/L), LDL-C will be measured via the beta quantification method (rather than the Friedewald formula). Non-HDL-C will be calculated by subtracting HDL-C from TC. Ratio ApoB/ApoA-1 will be calculated. All lipid results will be blinded from after randomization until the week 36 visit for the IV cohorts, and until database lock for the SC cohorts. No attempts should be made by the investigator or patient to have the patient's lipid values independently evaluated after randomization and through the EOS visit.

Detailed procedures of sample preparation, storage, and shipment are provided in the laboratory manual.

8.2.2.1. Core Lipid Panel

Fasting blood (at least 8 hours) samples for the core lipid panel (TC, TG, HDL-C, non-HDL-C, and calculated LDL-C) will be collected at time points described in [Table 1](#), [Table 2](#), [Table 3](#), [Table 4](#), [Table 5](#), [Table 6](#), and [Table 7](#). These samples will also be used for specialty lipid panel assessment when it is scheduled at the same time as the lipid panel assessment. All lipid results after the randomization visit will be blinded.

8.2.2.2. Specialty Lipid Panel

Fasting (at least 8 hours) blood samples for the specialty lipid panel (ApoB, ApoA-1, ApoB/ApoA-1 ratio, and Lp[a]), as well as for ApoCIII will be collected at time points according to in [Table 3](#), [Table 4](#), [Table 5](#), [Table 6](#), and [Table 7](#). The specialty lipid panels will be assessed in the same sample that is collected for the lipid panel. All lipid results will be blinded from after randomization until the week 36 visit for the IV cohorts, and until database lock for the SC cohorts

8.2.3. Safety Procedures

8.2.3.1. Vital Signs

Vital signs, including temperature, sitting blood pressure, pulse, and respiration rate, will be collected pre-dose at time points according to in [Table 1](#), [Table 2](#), [Table 3](#), [Table 4](#), [Table 5](#), [Table 6](#), and [Table 7](#). Post-dose vital signs consist of blood pressure and pulse rate and will be collected 30 minutes and 60 minutes after completion of the IV infusion.

Blood pressure should be measured in the same arm throughout the study, after the patient has been resting quietly for at least 5 minutes. Pulse rate will be measured at the time of the measurement of blood pressure.

8.2.3.2. Physical Examination

A thorough and complete physical examination will be performed at time points according to in [Table 1](#), [Table 2](#), [Table 3](#), [Table 4](#), [Table 5](#), [Table 6](#), and [Table 7](#). Care should be taken to examine and assess any abnormalities that may be present, as indicated by the patient's medical history.

8.2.3.3. Electrocardiogram

A standard 12-lead electrocardiogram (ECG) will be performed at time points according to in [Table 1](#), [Table 2](#), [Table 3](#), [Table 4](#), [Table 5](#), [Table 6](#), and [Table 7](#). Electrocardiograms should be performed before blood is drawn during visits that require blood draws.

The 12-lead ECGs should be performed in the supine position after resting for at least 10 minutes. For each ECG recording throughout the study, the electrodes should be positioned at the same place as much as possible. The ECG will be interpreted locally by the investigator. Any new and/or clinically significant changes in ECG parameters should be immediately rechecked for confirmation before making any decision for the concerned patient.

Any clinically significant abnormality should be documented as an AE/SAE, as applicable. Each ECG tracing will be analyzed in comparison with the screening recorded trace. All ECG tracings will be kept as source data (see Section [9.4.5](#)).

8.2.3.4. Laboratory Testing

All laboratory samples will be collected before the dose of study drug is administered.

Samples for laboratory testing will be collected at time points according to in [Table 1](#), [Table 2](#), [Table 3](#), [Table 4](#), [Table 5](#), [Table 6](#), and [Table 7](#) and analyzed by a central laboratory during the study. Detailed instructions for blood sample collection are in the laboratory manual provided to study sites and specific tests are listed below.

Tests will include:

Blood Chemistry

Sodium	Total protein, serum	Total bilirubin*
Potassium	Creatinine	Uric acid
Chloride	Blood urea nitrogen (BUN)	Creatine phosphokinase (CPK)
Bicarbonate	Aspartate aminotransferase (AST)	
Calcium	Alanine aminotransferase (ALT)	
Glucose	Alkaline phosphatase	
Albumin	Lactate dehydrogenase (LDH)	

Blood chemistry tests should be performed with fasting samples.

* Samples with elevated values are automatically fractionated

Hematology

Hemoglobin	Differential:
Hematocrit	Neutrophils
Red blood cells (RBCs)	Lymphocytes
White blood cells (WBCs)	Monocytes
Platelet count	Basophils
Reticulocyte count	Eosinophils
Red blood cell distribution width (RDW)	

Urinalysis

Color	Glucose	RBC
Clarity	Blood	Hyaline and other casts
pH	Bilirubin	Bacteria
Specific gravity	Leukocyte esterase	Epithelial cells
Ketones	Nitrite	Crystals
Protein	WBC	Yeast

Other Laboratory Tests

Other laboratory tests will be performed at time points shown in [Table 1](#), [Table 2](#), [Table 3](#), [Table 4](#), [Table 5](#), [Table 6](#), and [Table 7](#) are as follows: FSH, TSH, hs-CRP, HbA1c, and serum and urine pregnancy test.

Abnormal Laboratory Values and Laboratory Adverse Events

- All laboratory values must be reviewed by the investigator or authorized designee.
- Significantly abnormal test results that occur after start of treatment must be repeated to confirm the nature and degree of the abnormality. When necessary, appropriate ancillary investigations should be initiated. If the abnormality fails to resolve or cannot be explained by events or conditions unrelated to the study medication or its administration, the medical monitor must be consulted.
- The clinical significance of an abnormal test value, within the context of the disease under study, must be determined by the investigator.

Criteria for reporting laboratory values as an AE are provided in Section [9.4.5](#).

8.2.3.5. Pregnancy Testing

Women of childbearing potential will undergo pregnancy testing approximately every 4 weeks throughout the study from baseline through EOS. Pregnancy testing will be via a urine pregnancy test, except for the screening visit and EOS visit, which will be via a serum pregnancy test. During some follow-up visits, and in case of early termination, pregnancy testing may occur at home via a urine pregnancy test where the results will be reported to the clinical site by the patient.

8.2.4. Pharmacokinetic and Anti-Drug Antibody Procedures

8.2.4.1. Drug Concentration Measurements and Samples

Serum samples for assessment of evinacumab and alirocumab concentration will be collected at specified time points listed in [Table 3](#), [Table 4](#), [Table 5](#), [Table 6](#), and [Table 7](#).

Any unused samples collected for drug concentration measurements may be used for exploratory biomarker research or other investigations.

8.2.4.2. Anti-Drug Antibody Measurements and Samples

Serum samples for anti-evinacumab antibody (ADA) assessment will be collected at time points listed in [Table 3](#), [Table 4](#), [Table 5](#), [Table 6](#), and [Table 7](#). They will be collected pre-dose on days when study drug is administered.

Patients who exhibit a treatment-emergent or treatment-boosted positive ADA assay response with a titer >240 in their last sample analyzed and who do not participate in an open-label study will be followed until the titers are <240 or have returned to within 2 dilution steps from their baseline titer levels.

8.2.5. Pharmacodynamic Procedures

Blood samples for measurement of total ANGPTL3, free and total PCSK9, and lipid profile (core lipid panel, specialty lipid panel) will be collected at specified time points listed in [Table 1](#), [Table 2](#), [Table 3](#), [Table 4](#), [Table 5](#), [Table 6](#), and [Table 7](#). ANGPTL3 concentration in serum will be measured from the PK samples collected at the time points listed in [Table 1](#), [Table 2](#), [Table 3](#), [Table 4](#), [Table 5](#), [Table 6](#), and [Table 7](#).

8.2.6. Other Assessments

8.2.7. Review of Diet

Patients will be following a heart-healthy diet at the screening visit and will be asked to continue the dietary plan until the last study visit. Patients will be queried on compliance with the dietary plan during the double-blind treatment period, at time points according to [Section 8.1](#).

Details are provided in the study reference manual.

8.2.8. Low Density Lipid-Receptor Function

A blood sample for LDL-R function testing will be collected from a subset of patients at time points according to in [Table 3](#), and [Table 4](#) in order to characterize LDL-R function and explore potential differences in safety and efficacy.

8.2.9. Future Biomedical Research

Biomarker samples will be collected at time points according to [Table 1](#), [Table 2](#), [Table 3](#), [Table 4](#), [Table 5](#), [Table 6](#), and [Table 7](#). The biomarker samples unused for study-related research, as well as unused PK and ADA, will be stored for up to 15 years after the final date of the database lock. The unused samples may be utilized for future biomedical research of hyperlipidemia and other

related diseases. No additional samples will be collected for future biomedical research. After 15 years, any residual samples will be destroyed.

[REDACTED]

9. SAFETY DEFINITIONS, REPORTING, AND MONITORING

9.1. Obligations of Investigator

The investigator must promptly report to the Institutional Review Board (IRB)/Ethics Committee (EC) all unanticipated problems involving risks to patients. This includes death from any cause and all SAEs related to the use of the study drug. It is recommended that all SAEs be reported to the IRB/EC, regardless of assessed causality.

9.2. Obligations of Sponsor

During the course of the study, the sponsor will report in an expedited manner as per national regulatory requirements in participating countries, all SAEs that are both unexpected and at least reasonably related to the study drug (suspected unexpected serious adverse reaction, to the health authorities, IECs/IRBs as appropriate, and to the investigators.

Any AE not listed as an expected event in the Investigator’s Brochure or in this protocol will be considered as unexpected. Any worsening of or new onset of symptoms related to hypercholesterolemia which occur during the screening period prior to study drug administration will be considered expected.

In addition, the sponsor will report in an expedited manner all SAEs that are expected and at least reasonably related to the evinacumab to the health authorities, according to local regulations.

At the completion of the study, the sponsor will report all safety observations made during the conduct of the trial in the clinical study report to health authorities and IECs/IRB as appropriate.

9.3. Definitions

9.3.1. Adverse Event

An AE is any untoward medical occurrence in a patient administered a study drug, which may or may not have a causal relationship with the study drug. Therefore, an AE is any unfavorable and unintended sign (including an abnormal laboratory finding), symptom, or disease, which is temporally associated with the use of a study drug, whether or not considered related to the study drug.

An AE also includes any worsening (ie, any clinically significant change in frequency and/or intensity) of a pre-existing condition that is temporally associated with the use of the study drug.

9.3.2. Serious Adverse Event

An SAE is any untoward medical occurrence that at any dose:

- Results in **death** – includes all deaths, even those that appear to be completely unrelated to study drug (eg, a car accident in which a patient is a passenger).
- Is **life-threatening** – in the view of the investigator, the patient is at immediate risk of death at the time of the event. This does not include an AE that, had it occurred in a more severe form, might have caused death.
- Requires in-patient **hospitalization** or **prolongation of existing hospitalization**. In-patient hospitalization is defined as admission to a hospital or an emergency room for longer than 24 hours. Prolongation of existing hospitalization is defined as a hospital stay that is longer than was originally anticipated for the event, or is prolonged due to the development of a new AE as determined by the investigator or treating physician.
- Results in persistent or significant **disability/incapacity** (substantial disruption of one's ability to conduct normal life functions).
- Is a **congenital anomaly/birth defect**
- Is an **important medical event** - Important medical events may not be immediately life-threatening or result in death or hospitalization, but may jeopardize the patient or may require intervention to prevent one of the other serious outcomes listed above (eg, intensive treatment in an emergency room or at home for allergic bronchospasm; blood dyscrasias or convulsions that do not result in hospitalization; or development of drug dependency or drug abuse).

9.3.3. Adverse Events of Special Interest

An AE of special interest (AESI; serious or non-serious) is one of scientific and medical concern specific to the sponsor's product or program, for which ongoing monitoring and rapid communication by the investigator to the sponsor can be appropriate. Such an event might warrant further investigation in order to characterize and understand it. Depending on the nature of the

event, rapid communication by the study sponsor to other parties (eg, regulators) might also be warranted (Section 9.4.3).

9.3.4. Infusion Reactions

Infusion reactions are defined as any AE that occurs during the infusion or within 2 hours after the infusion is completed. All infusion reactions must be reported as AEs (defined in Section 9.4.1) and graded using the grading scales as instructed in Section 9.5.1.

9.4. Recording and Reporting Adverse Events

9.4.1. Adverse Events

The investigator (or designee) will record all AEs that occur from the time the informed consent is signed until the EOS. Refer to the study reference manual for the procedures to be followed.

Information on follow-up for AEs is provided in Section 9.4.6. Laboratory, vital signs, or ECG abnormalities are to be recorded as AEs as outlined in Section 9.4.5.

9.4.2. Serious Adverse Events

All SAEs, regardless of assessment of causal relationship to study drug, must be reported to the sponsor (or designee) within 24 hours. Refer to the study reference manual for the procedure to be followed.

Information not available at the time of the initial report must be documented in a follow-up report. Substantiating data such as relevant hospital or medical records and diagnostic test reports may also be requested.

In the event the investigator is informed of an SAE after the patient completes the study, the following will apply:

- SAE with an onset within 30 days of the EOS/early termination visit- the SAE will be reported to the sponsor. The investigator should make every effort to obtain follow-up information on the outcome until the event is considered chronic and/or stable.
- SAE with an onset day greater than 30 days from the EOS/early termination visit - only fatal SAEs and those deemed by the investigator to be drug-related SAEs will be reported to the sponsor. The investigator should make every effort to obtain follow-up information on the outcome of a drug-related SAE until the event is considered chronic and/or stable.

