9.4.3. Other Events that Require Accelerated Reporting to Sponsor

The following events also require reporting to the sponsor (or designee) within 24 hours of learning of the event:

Symptomatic Overdose of Study Drug: Accidental or intentional overdose of at least 2 times the intended dose of study drug within the intended therapeutic window, if associated with an AE

Pregnancy: Although pregnancy is not considered an AE, it is the responsibility of the investigator to report to the sponsor (or designee), within 24 hours of identification,

any pregnancy occurring in a female or female partner of a male, during the study or within 24 weeks of the last dose of study drug. Any complication of pregnancy affecting a female study patient or female partner of a male study patient, and/or fetus and/or newborn that meets the SAE criteria must be reported as an SAE. Outcome for all pregnancies should be reported to the sponsor

Adverse Events of Special Interest: All AESIs, serious and non-serious, must be reported within 24 hours of identification using the same reporting process as for SAE reporting, per Section 9.4.2.

Adverse events of special interest for evinacumab include the following:

- Anaphylactic reactions
- Allergic reactions and/or local injection site reactions that require medical treatment or consultation with another physician for further evaluation
- Increase in ALT or AST: ≥ 3 x ULN (if baseline < ULN), or ≥ 2 x baseline value (if baseline \geq ULN)
- Pregnancy
- Symptomatic overdose with IMP
- Neurocognitive events
- New onset of diabetes
- Pancreatitis

Adverse events of special interest for alirocumab include the following:

- Increase in ALT: ALT ≥ 3 x ULN (if baseline ALT < ULN), or ALT ≥ 2 x baseline value (if baseline ALT \geq ULN)
- Allergic events and/or local injection site reactions that require consultation with another physician for further evaluation
- Pregnancy
- Symptomatic overdose with IMP
- Neurologic events that require additional examinations/procedures and/or referral to a specialist
- Neurocognitive events
- Cataracts
- New onset of diabetes:

The definition of new onset of diabetes will be the following:

- Type 1 or type 2 diabetes treatment-emergent adverse event (TEAE) (grouping of MedDRA terms will be specified in the SAP)

and/or

- at least 2 values of HbA1c $\geq 6.5\%$ during the TEAE period

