4.8.1. Adverse Events Variables

The period of safety observation starts from the time when the patient gives informed consent and continues into the following periods:

- The PRE-TREATMENT period is defined from the day the ICF is signed to the day before the first dose of double-blind study treatment administration.
- The double-blind treatment-emergent adverse event (TEAE) period is defined from the day of the first dose of double-blind study treatment administration to the day of the last dose of double-blind study treatment administration + 168 days (24 weeks) (based on PK considerations, residual effect of study treatment might be observed until 24 weeks after the last dose of study drug) for those patients not proceeding into the OLTP (ie, Group A patients and Group B patients who prematurely discontinue study treatment), or up to the day before the first dose of open-label study treatment administration for those patients proceeding into the OLTP
- The open-label treatment-emergent adverse event (TEAE) period (Group B only) is defined from the day of the first open-label study treatment administration to the day of the last open-label study treatment administration + 168 days (24 weeks).
- The POST-TREATMENT period is defined from the day after the end of the respective TEAE periods to the last study visit.

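### The 30-day SAE cut-off in section 9.4.2 has an ambiguous anchor, and for double-blind withdrawers who miss the 24-week EOS visit it can leave most of the 168-day TEAE window without all-cause SAE reporting

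*Protocol*

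**What the plan says.** Protocol 9.4.2 starts from a general rule: "All SAEs, regardless of assessment of causal relationship to study drug, must be reported to the sponsor (or designee) within 24 hours". A second rule follows with its own lead-in: "In the event the investigator is informed of an SAE after the patient completes the study, the following will apply". That rule has two parts. In the first, "SAE with an onset within 30 days of the EOS/early termination visit- the SAE will be reported to the sponsor". In the second, "SAE with an onset day greater than 30 days from the EOS/early termination visit - only fatal SAEs and those deemed by the investigator" as drug-related are reported.

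Protocol 8.1.2 separates the two visits that 9.4.2 joins with a slash. A patient who leaves before the EOT visit is asked for two visits. For the early termination visit, "The EOT visit should take place within 5 days of treatment discontinuation, if possible". The EOS visit comes 24 weeks after the last dose. A patient who leaves after EOT (week 16 SC, week 24 IV) is asked only for an early termination/EOS assessment, also at 24 weeks. Protocol 6.3 asks for at least 24 weeks of follow-up after the last dose for anyone who leaves early.

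Under 9.4.1 the investigator "will record all AEs that occur from the time the informed consent is signed until the EOS", while 9.4.6 ends AE collection at the patient's last study visit. For patients who do not enter the open-label period, protocol 10.4.4.1 and SAP 4.8.1 run the double-blind TEAE period to the last dose + 168 days, because "based on PK considerations, residual effect of study treatment might be observed until 24 weeks after the last dose of study drug". For pregnancy, 9.4.3 already uses a dose-based limit: "during the study or within 24 weeks of the last dose of study drug".

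**The concern.** The early termination visit and the EOS visit can be months apart, so the choice of anchor decides how long non-fatal SAEs judged unrelated must be reported. If the early visit governs, reporting narrows long before the TEAE window closes.

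The analysis does not narrow with it. SAP 5.8.1 tabulates all serious TEAEs, shows relatedness in a separate table, and uses the whole safety set as denominator. Any Kaplan-Meier display of a selected TEAE censors an event-free patient at the end of the TEAE period, not at last contact. Time in which an unrelated non-fatal SAE need not be reported is therefore treated as observed and event-free. Serious TEAE incidence would be understated, and the investigator's causality call would become a condition for being counted.

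The plan foresees patients with short follow-up. Protocol 10.4.1 and SAP 4.5 count those whose last visit is less than 23 weeks after the last administration. Protocol 6.3 tells sites to trace patients who do not return through family, the private physician or registries. A site may thus hear of a non-fatal myocardial infarction or stroke and, on the early anchor, need not report it if it is judged unrelated.

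**Working it through.** This is calendar arithmetic.

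**The plan's own figure.** The TEAE window is W = 24 × 7 = 168 days. It matches the scheduled EOS:
- Group A: last dose day 106 + 168 = day 274, the EOS day in protocol Table 6.
- Group B: last open-label dose day 477 + 168 = day 645, the EOS day in protocol Table 7.

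For a patient who follows the schedule, reporting and analysis windows agree.

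**Inputs.** W = 168 days (10.4.4.1; SAP 4.8.1); cut-off 30 days after the anchoring visit (9.4.2); early termination visit within 5 days of stopping treatment (8.1.2); dosing interval up to 7 days SC and 28 days IV. Let v be the day of the anchoring visit, counted from the last dose.

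**Formulas.** All-cause reporting ends at v + 30. Restricted days = max(0, 168 − (v + 30)). Share = restricted days / 168.

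| Anchoring visit | v | All-cause reporting ends | Restricted days | Share |
|---|---|---|---|---|
| Early termination on the last-dose day | 0 | 30 | 138 | 82.1% |
| Early termination 5 days later | 5 | 35 | 133 | 79.2% |
| SC: one interval + 5 days | 12 | 42 | 126 | 75.0% |
| IV: one interval + 5 days | 33 | 63 | 105 | 62.5% |
| Half-window point | 54 | 84 | 84 | 50.0% |
| Late withdrawal visit (illustration) | 100 | 130 | 38 | 22.6% |
| EOS at 24 weeks | 168 | 198 | 0 | 0% |

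The SC and IV upper ends assume that the decision to stop comes no later than the next due dose. More than half of the window is restricted only if v is below 168/2 − 30 = 54 days.

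**Number of patients.** The documents give no rate for missed EOS visits. The only related figure is the 5% dropout in protocol 10.2: 0.05 × 252 = 12.6, or about 13. Used as a ceiling, it gives a range of 0 to 13.

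**The case against.** The strongest reply is that the plan already keeps withdrawn patients in view. Protocol 6.3 and 8.1.2 ask for 24 weeks of follow-up, four-weekly calls and an EOS visit. Section 9.4.1 and SAP 4.8.1.1 record AEs, serious ones included, to the end of study without a causality filter. Patients who only stop study drug stay in the study for all visits (7.4.2). The narrower rule in 9.4.2 is introduced for patients who have completed the study, which someone still awaiting an EOS visit has not. All of this stands for patients who attend EOS: none of their 168 days is lost.

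A reader might infer that every early withdrawer loses most of the window. The documents do not support that. Nor do they support adding open-label withdrawals: these come after week 24, and 8.1.2 then asks only for the 24-week visit, so they are unaffected if it takes place. Nothing in the documents shows that early withdrawers left because of an event.

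It can also be argued that the label in 9.4.2 means the 24-week visit, since 8.1.2 pairs early termination with EOS for later withdrawals. That reading is possible. But 8.1.2 also uses early termination for the visit due within 5 days of stopping, and the label has no clear meaning for a patient who attended that visit and missed EOS. For this patient the lead-in about completing the study does not settle the matter, and 9.4.6 lets AE collection end at the visit already made.

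Finally, where contact is lost altogether, SAEs go missing because nobody hears of them, not because of the rule. That is true, and it limits the gain from any rewording.

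**Conclusion.** The point holds for one group: patients who withdraw in the double-blind period, attend an early termination visit and do not attend the 24-week EOS visit. On the early termination anchor, all-cause SAE reporting ends at day 30 to 42 after the last dose for SC and day 30 to 63 for IV. Across both routes, 105 to 138 of 168 days (62.5% to 82%) are then limited to fatal or related SAEs, in conflict with the all-cause TEAE window and the 24-week follow-up. The figures assume that the visit falls within one dosing interval plus 5 days of the last dose; a later visit shrinks the gap.

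The size of the group is unknown. The ceiling of 13 of 252 assumes that every planned dropout misses EOS, and the 5% was set for the week 16 efficacy measure, not for loss from safety follow-up. It should not be read as an expected count. The primary endpoint is untouched and the safety summaries are descriptive. This is a defect in a stated rule that should be corrected because correction is cheap; it does not threaten the trial's main conclusion.

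**What to change.** In protocol 9.4.2, tie the date to the last dose. State that all SAEs, whatever their causality, are reported if onset is no later than 168 days after the last dose of study drug or 30 days after the EOS/early termination visit, whichever is later. Apply the restriction to fatal or drug-related SAEs only after that date. It then no longer matters inside the TEAE window which visit governs, and 9.4.2 agrees with 6.3, 8.1.2, 9.4.1, 10.4.4.1 and the 24-week pregnancy rule in 9.4.3.

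The cost is one amended sentence and a few extra SAE reports. No visits or procedures are added, so the gain is limited to SAEs that the site learns of through follow-up calls, tracing or chance contact.
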